4.12.5 Pharmacodynamic Parameters

DCR-AUD is designed to selectively reduce ALDH2 levels in the liver and the conversion of acetaldehyde to acetic acid. The build-up of acetaldehyde causes unpleasant effects after drinking (e.g., headache, facial flushing, tachycardia, nausea, vomiting). As such, the PD activity of DCR AUD will be assessed during EIAs using blood biomarkers (alcohol, acetaldehyde, and acetate), assessment of 6 symptoms and their severity induced during EIAs, and objective physiological biomarkers (heart rate and facial skin temperature). Participants' subjective experience of the effects

of alcohol will be assessed. Instructions for the collection and handling of biological samples will be provided by the Sponsor in the Laboratory Manual and the Laboratory Specification document.

PD parameters will be calculated using drug effect model from the biomarker time data using Phoenix® WinNonlin® 8.3 or higher. The biomarker parameters alcohol, acetaldehyde, and acetate unadjusted and adjusted for baseline will be estimated for treatment, nominal point, EIA days, and ALDH2 status. The Phoenix WinNonlin project file including all settings and analysis input file will be transferred to Dicerna when the biomarker PD analyses are completed.

The unadjusted and adjusted biomarker parameters will all be listed, and unadjusted parameters will be summarized by time point and treatment. Descriptive statistics (number, arithmetic mean, SD, CV%, geometric mean, gCV%, minimum, median, and maximum) will be presented by nominal points, treatment, ALDH2 status, and EIA days for absolute, and percentage change from the biomarker baseline, where appropriate. For time variables Tmin and Tmax, only median will be presented.

One way ANOVA model will be used to compare the unadjusted Biomarker parameters for DCR-AUD and Placebo for PP.

To visualize the comparison between treatment and placebo following alcohol consumption the following descriptive PD parameter graphs will be generated:

The mean (\pm SD) Cmax and AUC0-4h of acetaldehyde, acetate, and ethanol will be plotted with EIA days. Two mean Cmax figures will be prepared: one in μ M and another in ng/mL units.

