- ^m Participants may be discharged from clinic following collection of the 24-hour postdose PK sample. Participants will return to clinic for collection of PK samples at 72 hours postdose on Days 4 and 32.
- ⁿ EIA will be conducted on the first day of the visit once all other assessments for that day have been completed. A total of 10 EIAs will be conducted. The timing of assessments and ethanol administration are detailed in [Table 3](#).
- ^o On dosing days, ECGs will be conducted approximately 30 minutes predose and 15-to-30 minutes postdose. If multiple assessments are due, the order of assessment should be ECG, vitals, PK, and then other assessments; with PK sample collection occurring at the nominal time. At Screening and EOS, one ECG will be performed. Screening ECGs may be repeated one time for determination of eligibility.
- ^p Blood pressure, if out of range at Screening, may be repeated one time for determination of eligibility.
- ^q Blood pressure and pulse rate to be recorded 15 (\pm 5) minutes postdose.
- ^r Height will be measured and recorded at Screening. Weight will be measured and recorded at every visit.
- ^s Sample to be collected prior to ethanol administration.
- ^t Hematology to include complete blood count with differential and RBC indices. See [Section 10.2](#) for a complete list of parameters.
- ^u See [Section 10.2](#) for a complete list of parameters.
- ^v Blood samples for complement testing to be collected predose and 2, 8, and 24 hours postdose on Day 1 and Day 57.
- ^w Blood sample for ADA testing to be drawn at same time as predose PK sample on Day 1.
- ^x Plasma samples for PK analysis to be collected predose and at 1, 2, 4, 6, 8, 24, and 72 hours postdose (exception: no 72-hour PK sample is required at Day 57). A single sample will be collected on Day 168. If multiple assessments are due, the order of testing should be ECG, vitals, PK, and then other assessments, with the PK sampling performed preferably at the nominal time point. A \pm 15-minute window will be allowed for collections at 1, 2, 4, 6, and 8 hours postdose. A \pm 30-minute window will be allowed for collection at 24 hours postdose. A \pm 60-minute window will be allowed for collection at 72 hours postdose.
- ^y Participants to record any symptoms associated with use of alcohol outside of in-clinic EIAs. Diary to be issued at time of discharge from clinic and collected and reviewed upon return to clinic.

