3.2.5 Pharmacodynamic Variables

DCR-AUD is designed to selectively reduce ALDH2 activity in the liver and the conversion of acetaldehyde to acetic acid after alcohol consumption. The build-up of acetaldehyde causes unpleasant effects after drinking (e.g., flushing, headache, lightheadedness, palpitations, nausea, or

vomiting). As such, the PD activity of DCR-AUD will be assessed during EIAs via these 6 symptoms, and blood biomarkers (ethanol, acetaldehyde, and acetate) PD parameters to be estimated by Clinical Pharmacology, Modeling and Simulation (CPMS) group are provided in [Table 3-1](#).

Table 3-1 Plasma Pharmacodynamic Parameters

Protocol Parameter	WNL Name	Definition
t_{max}	Tmax	Time corresponding to occurrence of C_{max} (For acetaldehyde, acetate, and alcohol)
C_{max}	Cmax	Maximum observed concentration (in the unit of μM and ng/mL) (For acetaldehyde, acetate, and alcohol)
$C_{maxAbove}$	Cmax_Above_B	Maximum observed concentration that is above the baseline (in the unit of μM and ng/mL) (For acetaldehyde)
baseline	Baseline	Response value just prior to treatment administration
AUC_{Above}	AUC_Above_B	Area under the curve that is above the baseline (for acetaldehyde)
AUC_{Below}	AUC_Below_B	Area under the curve that is below the baseline (for acetate)
AUC_{0-4h}	AUCT	Observed partial area under the curve from time 0 to 4 hours (for acetaldehyde, acetate, and alcohol)
C_{av}	Cav	Average plasma concentration from time zero to 4 hours
PD response change	PD_response_change	Changes in each biomarker level on each EIA day (i.e., D1,14,29,42, 57) compared to the basal level on Day -1
PD response % change	PD_response_%_change	Percent changes in each biomarker level on each EIA day (i.e., D1,14,29,42,57) compared to the basal level on Day -1

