4.12.3 Statistical Analysis of Pharmacokinetic Parameters

We will use a one-way analysis of variance to compare the PK parameters of ALDH2 mutation. If there are 3 or more subjects with ALDH2 mutation, the PK parameters of these subjects as a group will be compared to those without ALDH2 mutation as another group. Otherwise, the PK parameters will be summarized with and without the individual(s) with ALDH2 mutation.

Sample SAS Code:

```
PROC MIXED DATA = DATA1 NOPRINT;
BY PARAMCD;
CLASS MUTATION;
MODEL LN_PK = MUTATION /DDFM = KR;
RUN;
```

WHERE,

PARAMCD :short name of PK parameter

LN_PK; natural log transformed value of PK parameter
MUTATION: Group for the genetic mutation.

4.12.4 Pharmacodynamic Analysis, Concentration, and Parameter TFLs, and Statistical Analysis of Pharmacodynamic Parameters

Pharmacodynamic parameters will be estimated according to the guidelines presented in Table 4-2.

Table 4-2 Pharmacodynamic Parameter and Estimation

Parameter	Guidelines for Derivation
Cmax, tmax,	Obtained directly from the observed concentration-time data
C_{av}	The average concentration from time 0 to time 4 h: $AUC_{0-4\text{ h}}$
$AUC_{0-4\text{ h}}$ -adjusted	The AUC adjusted from zero time to 4 h for Day X: $AUC_{0-4\text{ h}}(\text{Day X}) - AUC_{0-4\text{ h}}(\text{Day -1})$
C_{av} -adjusted	The C_{av} adjusted for Day X is time averaged concentration from zero time to 4 h: $C_{av}(\text{Day X}) - C_{av}(\text{Day -1})$
Cmax-adjusted	The Cmax adjusted for Day X is: $C_{max}(\text{Day X}) - C_{max}(\text{Day -1})$
$AUC_{0-4\text{ h}}$ percent change	Percent change of $AUC_{0-4\text{ h}}$ on Day X as compared to the basal level (Day -1): $((AUC_{0-4\text{ h}}(\text{Day X}) - AUC_{0-4\text{ h}}(\text{Day -1})/\text{day -1})) \times 100$
C_{av} percent change	Percent change of C_{av} on Day X as compared to the basal level (Day -1): $((C_{av}(\text{Day X}) - C_{av}(\text{Day -1})/\text{day -1})) \times 100$
Cmax percent change	Percent change of Cmax on Day X as compared to the basal level (Day -1): $((C_{max}(\text{Day X}) - C_{max}(\text{Day -1})/\text{day -1})) \times 100$

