Individual participant's biomarker (acetaldehyde, acetate, and ethanol) plasma concentration values (baseline unadjusted values only) will be provided by [REDACTED] Laboratories and [REDACTED]. Baseline unadjusted and adjusted acetaldehyde, acetate, and ethanol concentration values will be listed by study day, timepoint, ALDH2 mutation, and participant for the PP by [REDACTED]. Concentration listings will include nominal biomarker sampling time, actual sampling times relative to dose administration, and percentage change from baseline. The corresponding baseline for each timepoint will be taken on Day -1. For the biomarker concentration summary tables, descriptive statistics (N, n, arithmetic

mean, SD, CV%, geometric mean, gCV%, median, IQR (inter quartile range), minimum, and maximum values) will be presented by study day, nominal timepoint, EIA days, and ALDH2 mutation. For time variables only median, T_{min} and T_{max} will be presented. A by participant listing of ALDH2 mutation will be provided.

To visualize the comparison between study days the descriptive biomarker graphs will be generated.

- Figure x.x.x: Individual Participant Profiles for acetaldehyde, acetate, and ethanol, Plasma Concentration Time Data (Unadjusted and Adjusted for Baseline) by study day and EIA day (SP)
- Figure x.x.x: Overlaid Individual Participant Profiles for acetaldehyde, acetate, and ethanol Plasma Concentration Time Data (Unadjusted and Adjusted for Baseline) by study day and EIA day (SP). The profiles for ALDH2 mutation will be plotted with dotted lines.
- Figure x.x.x: Mean (\pm SD) baseline adjusted acetaldehyde, acetate, and ethanol Plasma Concentration Time Data by study day and EIA day (PP)
- Figure x.x.x: Mean (\pm SD) baseline adjusted acetaldehyde, acetate, and ethanol Plasma Concentration without ALDH2 Mutant Time Data by study day and EIA day (PP)
- Figure x.x.x: The Mean (\pm SD) baseline unadjusted acetaldehyde, acetate, and ethanol Plasma Concentration Time profiles by study day and EIA days (PP)
- Figure x.x.x: The Mean (\pm SD) baseline unadjusted acetaldehyde, acetate, and ethanol Plasma Concentration without ALDH2 Mutant Time profiles by study day and EIA days (PP)

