4.12.1.2 PD Biomarkers for EIA

4.12.1.2.1 EIA Blood Biomarkers

Blood biomarkers to be assessed include measurement of acetaldehyde, acetate, and ethanol. A by-participant listing of EIA blood biomarkers will be presented in SP. A summary table of Tmax, Cmax, and AUC0-2.5h of blood biomarkers will be presented by biomarker parameter, visit, time point, EIA days, treatment and placebo in PD population. The same PK parameter analysis method described in Section 4.10 will be applied to the calculations of these biomarker parameters.

The mean (\pm SD) plasma concentration – time profiles of these biomarkers will be plotted by treatment and EIA days.

The mean (\pm SD) Cmax and AUC0-4.0h of acetaldehyde, acetate, and ethanol will be plotted with EIA days by treatment.

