4.15 Biomarkers

4.16 Adjustments for Covariates

Not applicable

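### The SAP's only between-arm model for the EIA biomarkers leaves out the Day -1 EIA, giving up precision and protection against chance imbalance with four placebo participants

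*SAP*

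**What the plan says.** SAP 4.12.5 names one model that compares the arms on the EIA biomarkers: "One way ANOVA model will be used to compare the unadjusted Biomarker parameters for DCR-AUD and Placebo for PP". PP is the pharmacodynamic population. The same section speaks of parameters unadjusted and adjusted for baseline, so the meaning of the word is clear. SAP 4.16 plans no covariates: "Adjustments for Covariates Not applicable".

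Elsewhere the biomarker reference is the Day -1 EIA, done before any study drug:

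- SAP Table 4-2 defines adjusted and percent-change AUC0-4h, Cav and Cmax against Day -1, for example "Percent change of Cmax on Day X as compared to the basal level (Day -1)".
- SAP 4.12.4, on concentrations: "The corresponding baseline for each timepoint will be taken on Day -1".
- SAP Table 3-1, on PD response change: "Changes in each biomarker level on each EIA day (i.e., D1,14,29,42, 57) compared to the basal level on Day -1".

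Table 3-1 also has a separate baseline row, defined as the response immediately before treatment is given.

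The Protocol's Schedule of Activities says "A total of 10 EIAs will be conducted". One is on Day -1, so nine follow dosing. Protocol 9.1 plans descriptive statistics without inferential tests, and Protocol 9.4.3.2 asks for descriptive statistics and change from baseline. SAP 4.21 records no change to the planned analysis.

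**The concern.** One stated purpose of the study (SAP 1) is to see whether a PD effect appears during EIAs after repeat dosing. For the biomarkers, the 4.12.5 model is the only one that sets DCR-AUD against placebo. Every participant is scheduled for a Day -1 EIA, and the SAP derives Day -1-adjusted parameters, but this model uses neither.

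With 12 versus 4 participants the interval is wide in any case. Two things are at stake. A covariate related to the outcome could narrow that interval. And with four controls, a chance difference between the arms on Day -1 carries into the unadjusted comparison. Such a difference would be visible in the trial's own Day -1 data, so a reader could challenge the unadjusted result.

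**Working it through.** **Inputs.** From the documents: 12 active and 4 placebo (Protocol 9.2, SAP 4.20). Assumed: one record per participant per EIA, log scale, equal SD in both arms and at both EIAs, and a Day -1 to post-dose correlation ρ. The documents give no ρ, SD, effect size or power, so there is no planned figure to reproduce. Results are in units of the between-participant SD at one EIA.

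**Formulas.**

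- ANOVA: SE = √(1/12 + 1/4) = 0.577, with 14 df. Half-width = 2.145 × 0.577 = 1.24.
- ANCOVA: SE ≈ √[(1 − ρ²)(1/12 + 1/4)(1 + 1/12)], with 13 df. At ρ = 0.5 this is 0.520, and the half-width is 2.160 × 0.520 = 1.12.
- Change from Day -1: SE = √[2(1 − ρ)(1/12 + 1/4)]. At ρ = 0.3 this is 0.683, and at ρ = 0.5 it is 0.577. Below 0.5 it is worse than the ANOVA.

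**Mean half-width by simulation** (100,000 trials per ρ). These values sit slightly below the formulas because the estimated SD averages about 0.98 of the true SD at 13 to 14 df.

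| Assumed ρ | ANOVA | ANCOVA | Ratio |
|---|---|---|---|
| 0 | 1.22 | 1.27 | 1.045 |
| 0.3 | 1.22 | 1.21 | 1.00 |
| 0.5 | 1.22 | 1.10 | 0.91 |
| 0.7 | 1.22 | 0.91 | 0.75 |
| 0.8 | 1.22 | 0.76 | 0.63 |

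Break-even: 1.045 × √(1 − ρ²) = 1 gives ρ = 0.29.

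**In ratio terms.** An assumed between-person CV of 30% is a log SD of √ln(1 + 0.3²) = 0.294. The ANOVA interval then multiplies or divides the geometric mean ratio by exp(1.22 × 0.294) = 1.43. With ANCOVA the factor is 1.38 at ρ = 0.5 and 1.31 at ρ = 0.7.

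**Chance imbalance.** A Day -1 difference between arms above 0.5 SD has probability 2[1 − Φ(0.5/0.577)] = 39%. A difference above one SE (0.577 SD) has probability 2[1 − Φ(1)] = 32%. Overall, both models reject a true null about 5% of the time. Among trials with imbalance above one SE, the ANOVA rejects in about 9% at ρ = 0.5 and 12% at ρ = 0.7; the ANCOVA stays near 5%.

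**Unequal slopes.** If the drug halves the active-arm slope, the ANCOVA half-width is 1.25 / 1.21 / 1.15 / 1.11 SD at placebo correlations of 0.3 / 0.5 / 0.7 / 0.8. That is a small loss at 0.3, break-even just under 0.5, and a gain of at most 1 − 1.11/1.22 = 9%.

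**Missing Day -1 value.** SAP 4.2.4 does not impute a missing baseline. If one placebo participant lacks a Day -1 value, the ANCOVA at 12 versus 3 and ρ = 0.5 has half-width 1.24 SD, against 1.22 SD for the ANOVA on all 16.

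**The case against.** The strongest reply is that this is a preference for precision, not an error. The per-EIA ANOVA is valid, the gain depends on a correlation the documents do not give, and below about 0.3 the ANCOVA is slightly worse. If the drug works by weakening the link to Day -1, break-even rises to nearly 0.5. All of that stands.

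It also stands that Day -1 is not ignored. SAP 4.12.5 describes percent change from the biomarker baseline by treatment and EIA day, adjusted parameters are listed, and SAP 4.12.4 plots baseline-adjusted means. A reader might infer that Protocol 9.4.3.2 is not met; the descriptive outputs meet it. The principal secondary endpoint is the symptom score (Protocol 9.4.3), not these biomarkers.

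A simpler remedy would be to delete the ANOVA, since Protocol 9.1 plans no inference. That would remove the conflict, but it would leave no between-arm estimate with an interval for the biomarkers. A descriptive interval that uses Day -1 serves the study's question better.

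A reader might also count other loose ends as support. The 4.12.5 sentence gives no scale and no list of EIAs. Table 3-1's list of days stops at 57, but it belongs to the response-change rows, not to the ANOVA. The BLQ rules in SAP 4.12.1 and 4.12.2 differ because one serves summary tables and the other parameter derivation. These are missing details or editorial points, and they say nothing about whether Day -1 belongs in the model.

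**Conclusion.** The point holds as a modest, inexpensive improvement to a secondary analysis. The one model comparing the arms on the biomarkers omits a baseline that the SAP uses elsewhere. With equal slopes, adding it narrows the interval by about 9%, 25% and 37% at assumed correlations of 0.5, 0.7 and 0.8, makes almost no difference at 0.3, and widens it by about 4.5% at zero. It also keeps the error rate near 5% when the arms happen to differ on Day -1.

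A reader might infer that the ANOVA is biased or has inflated type I error. The documents do not support this: randomisation keeps the overall rate at about 5%, and the 9% and 12% figures apply only to trials with an observed imbalance above one SE. Nor is it established that the sentence pools repeated EIAs as independent records. It does not say, and because the surrounding summaries are by EIA day, a separate analysis at each EIA is the likelier reading.

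The size of the gain rests on the assumed correlation, a common slope in both arms and complete Day -1 data. No primary safety conclusion changes.

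**What to change.** In SAP 4.12.5, replace the ANOVA sentence with:

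> For each analyte and each post-dose EIA, log Cmax and log AUC0-4h will be compared between DCR-AUD and placebo by ANCOVA with treatment and the log Day -1 EIA value of the same parameter as terms. Geometric mean ratios with 95% CIs are descriptive, without p-values or multiplicity adjustment. Participants without a Day -1 value are left out of this model and counted by arm; the unadjusted comparison is shown alongside.

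Also:

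- State that baseline for this model is the Day -1 EIA parameter, not the immediate pre-treatment value in Table 3-1.
- Set one BLQ rule, the same for Day -1 and all later EIAs, that gives positive values for the log. This is a new rule; SAP 4.12.2 does not supply one, since it also uses zero and missing.
- Name the covariate in SAP 4.16.
- Record in SAP 4.21 that a model-based comparison was added to the descriptive plan of Protocol 9.1.

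As a separate correction in SAP 4.12.1.2.1, reconcile the summary ("A summary table of Tmax, Cmax, and AUC0-2.5h of blood biomarkers will be presented") with the plot ("Cmax and AUC0-4.0h of acetaldehyde, acetate, and ethanol will be plotted with EIA days by treatment"); Tables 3-1 and 4-2 define only the 4-hour AUC. Correct the reference there to Section 4.10, which reads as not applicable.

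Cost: SAP wording and one simple model per parameter and EIA, with no new data. It takes one degree of freedom (14 to 13). Intervals are about 4.5% wider if the correlation is near zero, and there is a small loss at low correlation if slopes differ. Any participant without a Day -1 value drops out of the model, which is why the unadjusted result stays alongside. The descriptive label matters: 3 analytes × 2 parameters × 9 EIAs = 54 intervals, of which about 54 × 0.05 = 2.7 would exclude 1 by chance under either model if the drug had no effect.

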4.12.1.1 Ethanol Interaction Assessments

EIAs will include an active assessment of the six key symptoms (flushing, headache, palpitations, lightheadedness, nausea, and vomiting) that DCR-AUD may induce, in order to determine what dose of DCR-AUD gives the proper constellation of these symptoms.

These symptoms will be collected by active questioning of each participant at different time points during each EIA i.e. before alcohol administration, at 0 minutes, 15minutes, 30 minutes, 45 minutes, 60 minutes, 90minutes, 120 minutes and 150 minutes after study drug administration. Should an EIA be missed, due to COVID-19 or other circumstances, the missed EIA may be conducted at the next scheduled visit or at an unscheduled visit at the discretion of the Investigator.

The following symptom scoring framework would be described as an arbitrary point system, where:

Symptom	No Symptom	Mild symptom	Moderate symptom	Severe symptom
Score	0	1	2	3

Each participant at each timepoint in an EIA after alcohol administration begins will be given a composite score for that timepoint as sum of all six symptom scores.

Baseline for EIA is defined as last non-missing value prior to alcohol administration.

Descriptive statistics of EIA composite score (n, mean, median, Q1 (25 percentile), Q3 (75 percentile), minimum and maximum) for absolute values and changes from baseline will be presented by, treatment, placebo, visit and time point.

Descriptive statistics of Peak EIA composite score (n, mean, median, Q1, Q3, minimum and maximum) for absolute values and changes from baseline will be presented by, treatment, placebo, and visit (Days).

Descriptive statistics of Peak EIA score in a Day (Column U) (n, mean, median, Q1, Q3, minimum and maximum) for absolute values and changes from baseline will be presented by, treatment, placebo, and visit (Days).

Peak EIA composite score is defined as maximum composite score at each visit.

To visualize participant-level composite score and the comparison between treatment the EIA graphs listed below will be generated.

- Figure xx.1: Combined Individual DCR-AUD and placebo EIA composite score-Time Profiles (Linear Scale) by Treatment, (Safety Population)
- Figure xx.1: Combined Individual DCR-AUD and placebo Peak EIA composite score-Visit (Days). Profiles (Linear Scale) by Treatment, (Safety Population)
- Figure xx.1: Combined Individual DCR-AUD and placebo Peak EIA score in a Day (Column U)-Visit (Days). Profiles (Linear Scale) by Treatment, (Safety Population)

Serial EIAs will be performed in designated participants to assess the indirect PD effects of ALDH2 reduction (acetaldehyde increase), including plasma acetaldehyde, acetate, and ethanol levels, induced symptoms, heart rate, facial skin temperature, and subjective feelings of alcohol intoxication or intolerance. Adverse events, vital signs, and ECG will also be monitored and recorded for safety.

To be clear, of interest would be 2 things in addition to plots above:

- o At each EIA, change in peak symptom score from baseline after alcohol administration from pre-administration score on that day
- o For each EIA change in the peak symptom score on that test day after alcohol administration from the peak score change on day -1 (i.e. On day of EIA challenge before IMP was administered)

(It is expected that most participants would have Day -1 pre-EIA challenge composite score of zero (0), i.e. Reporting none of 6 active surveillance symptoms before IMP and before any alcohol was administered on day -1. However, to the extent that some or few patients might have some symptoms, the most informative change metric that would reflect what the participant experiences is the change in peak composite score at any given EIA after dosing from that pre-IMP and pre-alcohol, i.e. Baseline score at day -1.)

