8.6.1.2. EIA Physiologic Signs and Symptoms

EIA assessments will include the direct questioning of participants as to the presence of ethanol reaction symptoms (flushing, headache, lightheadedness, palpitations, nausea, and vomiting) at the times indicated in [Table 3](#). Note: the presence of these ethanol reaction symptoms will not be considered AEs.

A composite 6-symptom score for each participant during each EIA will be determined as follows:

- At each of the timepoints during the EIA, each symptom will be given a numeric score of 0 (not present) to 3 (present and severe), with the exception of vomiting, which will be given a score of 3.
- The composite symptom score for each of the EIA timepoints will be the summed value for each of the 6 symptoms at that timepoint (range 0 – 18).
- The Peak score for a given day's EIA will be the participant's highest post-alcohol ingestion timepoint score minus the participant's pre-alcohol score.

Vital signs (BP and heart rate) and standard 12-lead ECGs will be recorded at the times indicated in [Table 3](#).

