9.4.3. Secondary Endpoints

PD analyses will be performed on the Pharmacodynamic Population, and PK analyses will be performed on Pharmacokinetic Population. Actual sampling times will be used for all parameter estimations. The principal secondary endpoint of interest will be the change from baseline in the composite 6-symptom score after EIAs (as described in [Section 8.6.1.2](#)).

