9.4.3.1. EIA Composite Score

EIAs will include an active assessment of the 6 key symptoms (flushing, headache, palpitations, lightheadedness, nausea, and vomiting) that DCR-AUD may elicit, in order to determine if the protocol-specified DCR-AUD dose regimen gives the proper constellation of these symptoms. These symptoms will be collected by active questioning of each participant at different time points during each EIA.

The following symptom scoring framework would be described as an arbitrary point system, where:

Symptom	No Symptom	Mild symptom	Moderate symptom	Severe symptom
Score	0	1	2	3

Each participant at each timepoint in an EIA after alcohol administration will be given a composite score for that timepoint as sum of all 6 symptom scores.

Baseline is defined as last non-missing value prior to alcohol administration.

Descriptive statistics of EIA composite score (n, mean, median, IQR [Inter Quartile Range], minimum and maximum) for absolute values and changes from baseline will be presented by treatment, placebo, visit, and time point.

Descriptive statistics of Peak EIA composite score (n, mean, median, IQR, minimum and maximum) for absolute values and changes from baseline will be presented by treatment, placebo, and visit (Days). The Peak EIA composite score is defined as maximum composite score at each visit.

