3.2.2 Secondary Endpoints

- Change in the occurrence and/or severity of 6 symptoms related to plasma acetaldehyde accumulation observed during in-clinic EIAs over the course of the study
- Change in plasma PD biomarker assessments during serial EIA
 - acetaldehyde
 - acetate
 - ethanol
- Plasma PK parameters of DCR-AUD

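### The SAP's derivation of the 6-symptom EIA score does not match the protocol section that defines the principal secondary endpoint

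*SAP*

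**What the plan says.** Protocol 9.4.3 states: "The principal secondary endpoint of interest will be the change from baseline in the composite 6-symptom score after EIAs", and refers to 8.6.1.2 for the description. Section 8.6.1.2 scores each symptom from 0 to 3, "with the exception of vomiting, which will be given a score of 3". The composite at a timepoint is "the summed value for each of the 6 symptoms at that timepoint (range 0 – 18"). The Peak score for a day is the participant's "highest post-alcohol ingestion timepoint score minus the" pre-alcohol score, so it is already a change.

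Protocol 9.4.3.1 gives a 0/1/2/3 table for all symptoms with no exception for vomiting. It adds: "The Peak EIA composite score is defined as maximum composite score at each visit". It also says: "Baseline is defined as last non-missing value prior to alcohol administration". Both the timepoint composite and the Peak are then summarised as absolute values and as changes from that baseline.

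SAP 3.2.2 gives the endpoint only in general terms: "Change in the occurrence and/or severity of 6 symptoms related to plasma acetaldehyde accumulation observed during in-clinic EIAs over the course of the study". SAP 4.12.1.1 repeats the table, the raw-maximum Peak and the pre-alcohol baseline of protocol 9.4.3.1. It then lists two comparisons of interest: same-day peak against the same-day pre-alcohol score, and test-day peak against the peak change on Day -1. A parenthesis that follows rates a third as most informative: "the change in peak composite score at any given EIA after dosing from that pre-IMP and pre-alcohol, i.e. Baseline score at day -1".

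SAP 4.12.1.2.2 lists vomiting with the other five symptoms as graded mild, moderate or severe, and defines three quantities:

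- Delta 1: peak minus same-day pre-alcohol score.
- Delta 2: peak minus Day -1 peak.
- Delta 3: a participant's highest Delta 1 over six tests after DCR-AUD, to be shown by treatment and visit.

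**The concern.** The study is run to see whether repeat dosing produces an observable PD effect during EIAs, and this score is the protocol's lead measure of the symptom part. Two programmers working from the same records, one from protocol 8.6.1.2 and one from the SAP, could produce different composites, different absolute Peaks and different Delta 3 values. If the rule is settled only when the tables are built, it may be settled with data in view. With four participants on placebo, one participant's score weighs heavily in that arm's mean.

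**Working it through.** **Inputs.** Scoring rules: protocol 8.6.1.2 and 9.4.3.1, SAP 4.12.1.1 and 4.12.1.2.2. Arm sizes 12 and 4: protocol 9.2. Ten EIAs, held on the first day of each visit: protocol Table 1, footnote n. The symptom records below are assumed examples; the documents give no symptom data.

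**1. The stated range.** Six symptoms at 0 to 3 give 0 to 6 × 3 = 18. Five symptoms at 0 to 3 plus vomiting at 0 or 3 also give 0 to 5 × 3 + 3 = 18. The range of 0 to 18 is reproduced under both vomiting rules, so it cannot show which is meant. It does show that absent vomiting must score 0, since otherwise the minimum would be 3.

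**2. Vomiting.** Take flushing 1, nausea 2 and one mild vomiting episode.

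- Flat rule: 1 + 2 + 3 = 6.
- Graded rule: 1 + 2 + 1 = 4.

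The gap is 3 − 1 = 2 points if mild, 3 − 2 = 1 if moderate and 3 − 3 = 0 if severe. A participant's Peak moves by at most the same amount, and by less if another timepoint holds the maximum. The arm mean moves, per such participant, by up to:

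| Grade | DCR-AUD (n = 12) | Placebo (n = 4) |
|---|---|---|
| Mild | 2/12 = 0.17 | 2/4 = 0.50 |
| Moderate | 1/12 = 0.08 | 1/4 = 0.25 |

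**3. Peak.** Take a pre-alcohol score of 1 and a post-alcohol maximum of 6.

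- Raw maximum (9.4.3.1 and SAP): Peak = 6, change from baseline = 6 − 1 = 5.
- Net (8.6.1.2): Peak = 6 − 1 = 5.
- Net Peak placed in a table that also reports change from baseline: 5 − 1 = 4, which removes the pre-alcohol score twice.

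The two definitions differ by exactly the same-day pre-alcohol score. The same-day change is 5 under both if it is subtracted once.

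**4. Change metrics.** Record A: Day -1 pre 0, maximum 3; Day X pre 2, maximum 5. Record B: pre 0, maximum 3 on both days.

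| Metric | Record A | Record B |
|---|---|---|
| Delta 1 (also the SAP's first comparison) | 5 − 2 = 3 | 3 − 0 = 3 |
| Peak minus Day -1 pre-alcohol score | 5 − 0 = 5 | 3 − 0 = 3 |
| Delta 2 | 5 − 3 = 2 | 3 − 3 = 0 |
| Second comparison, read literally | 5 − (3 − 0) = 2 | 3 − (3 − 0) = 0 |
| Second comparison, change minus change | (5 − 2) − (3 − 0) = 0 | (3 − 0) − (3 − 0) = 0 |

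With zero pre-alcohol scores on both days the list collapses to two values: the same-day rise, and the rise relative to the Day -1 peak.

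**5. Number of tests in Delta 3.** Days -1, 28 and 56 (first day of each dosing visit) give 3. The six visits of protocol Table 2 (Weeks 2, 6, 10, 12, 16 and 20) give 6, and Day 168 gives 1. The total is 3 + 6 + 1 = 10, which agrees with footnote n. Without Day -1, 10 − 1 = 9 are post-dose, not six. If a participant's largest Delta 1 fell in one of the three EIAs left out, Delta 3 would be too small. Delta 3 is also one value per participant, so it cannot vary by visit.

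**The case against.** The strongest reply is that the protocol already settles most of this. Section 9.4.3 points to 8.6.1.2, whose specific vomiting exception can govern the general table in 9.4.3.1. The tables in 9.4.3.1 and SAP 4.12.1.1 are silent on vomiting and do not contradict it. That covers the protocol but not the SAP, which nowhere carries the exception and in 4.12.1.2.2 expressly includes vomiting among graded symptoms. It also stands that the effect depends on how vomiting is recorded. If the case report form takes only yes or no, no mild grade arises; the documents do not show the form.

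Some stronger readings are tempting but not supported:

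- A reader might infer that the secondary endpoint has no planned analysis because SAP 4.10 reads Not Applicable. SAP 4.9 says the same for the primary objective, yet safety is fully specified in 4.13; the symptom analyses are in 4.12.1.1 and 4.12.1.2.2.
- A reader might infer that the SAP has replaced the protocol's endpoint with the metric it rates as most informative. That remark is a parenthesis, no listed Delta uses it, and Delta 1 is to be reported.
- A reader might infer that the protocol fixes Delta 1 as principal. Section 9.4.3 speaks of change in the composite, and 8.6.1.2 defines both a timepoint composite and a Peak, so Delta 1 is only the closest match.
- A reader might take the six tests of Delta 3 to be the six Table 2 visits. Nothing in the SAP says so; the text shows only a wrong count.
- The SAP's Peak score tagged Column U is not defined in the text, but may be defined in the table shells, which are not available here.

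**Conclusion.** The mismatch stands and should be fixed. As written, the SAP gives a composite that can differ from that of protocol 8.6.1.2, leaves Peak with two meanings, and defines Delta 3 over a number of tests that does not exist.

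The vomiting effect is limited to 2 points per report on an 18-point scale and assumes that a grade is recorded. The double subtraction equals the pre-alcohol score and vanishes when that score is 0. The SAP expects a score of 0 for most participants on Day -1; it makes no such statement for later EIAs. The missing choice of metric is the lesser point, because most of the metrics coincide at zero pre-alcohol scores and Deltas 1 to 3 are all to be shown.

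A reader might infer a threat to the trial's error rates. There is none: the symptom score receives only descriptive statistics in both documents, and the sample size rests on no calculation, so alpha, power and the 16 participants are unaffected. What is at stake is a reproducible derivation fixed before the data are seen.

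**What to change.** In the SAP:

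1. Carry over the 8.6.1.2 rule: vomiting scores 0 if absent and 3 if present. Keep any recorded grade in the listings.
2. Call the raw maximum the Peak composite score. Derive the same-day change once, as a separate variable (Delta 1 = raw maximum minus same-day pre-alcohol score), and state that it equals the Peak score of protocol 8.6.1.2.
3. Define Delta 3 over all post-dose EIAs (9 planned) and tabulate it by arm only.
4. Name the change metric that implements the principal secondary endpoint, and reconcile or remove the parenthesis on the most informative metric. Delta 1 at every EIA including Day -1 is closest to 8.6.1.2; the choice is the sponsor's. State whether the second comparison is a change minus a change.

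The cost is wording and minor reprogramming, with no new data. It can be done in a new SAP version or, after finalization, through the Statistical Method Modification Form that SAP section 1 names. Any departure from protocol text belongs in SAP 4.21, which now records none. Protocol 9.4 leaves technical detail to the SAP, so this need not wait for a protocol change; correcting 9.4.3.1 itself would be an amendment, for which protocol 10.1.1 sets the IRB/IEC approval requirement. The small downside is that vomiting severity no longer contributes to the composite.
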